 At each time point, growth measurements (recumbent length or height, weight and head circumference) will be measured 3 times in a row and averaged. All measurements should be recorded to the nearest tenth of a centimeter. The measurement of recumbent length or height, weight and head circumference should be performed by an individual, who does not have access to the records of the patient's earlier measurements in the study and, as far as possible, by the same individual at each patient visit.

 Bayley-III is to be discontinued when the patient reaches 42 months of age. The Bayley-III will be administered to patients from 1 month of age until the maximum score on each of the 3 administered scales has been obtained. Once the maximum score for a scale has been achieved, only the remaining scales will be administered.

 Additional anti-alglucosidase alfa IgG antibody testing should be performed upon determination of any notable deterioration in a patient's motor function.

 Modified Leiter-R Scale or updated Leiter-3 Scale assessment is to be performed at the last assessment of the Bayley-III Cognitive and Language Scales prior to the patient reaching 42 months of age and annually thereafter until the patient reaches the end of the follow up period. If previous assessments have been performed using Leiter-R and switch to Leiter-3 Scale is planned, then both assessments need to be performed at the same time of the initial administration of the Leiter-3, in order to create a baseline. The dates of the two tests should be recorded appropriately in the CRFs and the scores recorded on the appropriate test score sheets.

 Oligosaccharide (Hex4) testing will be performed every 6 months until the 24th month and then yearly.

 Genzyme Corporation or their designee will perform the CRIM analysis in skin biopsies. CRIM will be conducted only if written results are not available.

 GAA mutation analysis is to be conducted only if written results are not available.

 To be collected every 3 months up to Study Month 24 (3, 6, 9, 12, 15, 18, 21 and 24) and annually thereafter. Additional testing should be performed upon determination of any notable deterioration in a patient's motor function. Serum IgG samples should always be collected pre-infusion at each time point.

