### **9.3.5 Safety Laboratory Assessments**

Safety laboratory assessments will be performed pre-infusion at the times specified in [Table 9-1](#). The following chemistry and urinalysis variables will be measured:

- Blood urea nitrogen (BUN), creatinine, glucose, uric acid, calcium, phosphorus, albumin, total protein, sodium, potassium, chloride, bicarbonate, serum glutamic oxaloacetic transaminase (SGOT), serum glutamic pyruvic transaminase (SGPT), alkaline phosphatase, total bilirubin, creatine kinase (CK), and creatine kinase muscle, brain isoform (CK-MB).
- Complete blood count with differential.
- Urine appearance, specific gravity, pH, protein, glucose, ketones, bilirubin, and blood. Microscopy will be performed if clinically indicated.

Analysis of blood and urine samples will be conducted and reported by each participating site's laboratory. The Investigator should review lab reports in a timely manner.

The Investigator must indicate if out of range laboratory values are either clinically significant (CS), or not clinically significant (NCS). It is anticipated that some laboratory values may be

outside of the normal value range due to the underlying disease. As in routine practice the Investigators should use their clinical judgment when considering clinical significance. Clinical significance is defined as any variation in laboratory parameters, which has medical relevance and may result in an alteration in medical care. If CS laboratory changes from Baseline are noted, the changes will be documented on the AE CRF. The Investigator will also assess the relationship of all clinically significant out of range values to alglucosidase alfa as being not related, remote/unlikely, possible, probable, or definite. The Investigator will continue to monitor the patient with additional laboratory assessments until (1) values have reached normal range and/or Baseline, or, (2) in the judgment of the Investigator, out of range values are not related to the administration of alglucosidase alfa or other protocol-specific procedures.

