4.7.3 Additional safety assessments

4.7.3.1 Laboratory variables, vital signs, physical examinations (PE), and electrocardiograms (ECGs)

The following laboratory variables, vital signs, physical examinations (PE), and electrocardiogram (ECG) variables will be analyzed.

- Hematology:
 - Complete blood count with differential
- Clinical chemistry:
 - Metabolism: glucose, total protein, albumin, creatine kinase (CK), creatine kinase MB (creatine kinase muscle, brain isoform [CK-MB]), creatine kinase MB/total creatine kinase
 - Electrolytes: sodium, potassium, chloride, calcium, phosphorus, bicarbonate
 - Renal function: creatinine, blood urea nitrogen (BUN), uric acid (urate)
 - Liver function: alanine aminotransferase (ALT) [serum glutamic pyruvic transaminase (SGPT)], aspartate aminotransferase (AST) [serum glutamic oxaloacetic transaminase (SGOT)], alkaline phosphatase, total bilirubin

- Urinalysis:
 - Urinalysis for quantitative analysis: urine appearance, specific gravity, pH, protein, glucose, ketones, bilirubin, and blood.
 - Microscopy will be performed if clinically indicated.
- Vital signs: heart rate, systolic and diastolic blood pressure, respiratory rate, and temperature
- PE body systems: General Appearance, Skin, HEENT, Lymph Nodes, Heart, Lungs, Breasts, Abdomen, External Genitalia, Pelvic, Rectal, Extremities/Joints, Neurological, Mental Status examinations
- 12-lead ECG variables:
 - Intervals and measurements: heart rate, RR, PR, QRS duration, QRS axis, QT, QTc (Bazett and Fridericia correction)
 - Findings: sinus rhythm, LVH, RVH, conduction abnormalities

For summary tables, data below the lower limit of quantitation/detection limit (LLOQ) will be replaced by half of the LLOQ, while data above the upper limit of quantification (ULOQ) will be replaced by ULOQ value.

Analyses of quantitative variables

For all laboratory variables and quantitative ECG variables (intervals and measurements) above, descriptive statistics for results and changes from baseline will be provided for each planned visit during the on-treatment period. Vital signs data will be provided in a listing.

PE findings

PE findings (normal, abnormal, not examined) for each body system will be presented in a listing.

Analyses of ECG findings

For ECG, the incidence of patients with at least one abnormal ECG during the treatment-emergent period will be summarized according to the following baseline status categories:

- Normal/missing
- Abnormal

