5.4.3 Analysis windows for time points

The following analysis windows will decide how the scheduled and/or unscheduled visits will be used in the by-visit analyses of efficacy, safety, and exploratory variables.

A measurement (scheduled or unscheduled) will be used if it is available and measurement date is within the analysis window.

After applying these time windows, if multiple assessments are associated to the same time point, the closest from the targeted study day will be used. Except where specified otherwise, if the difference is a tie, the value after the targeted study day will be used. If multiple valid values exist within a same day, then all the valid values of the day will first be averaged before applying the

aforementioned rules. (Note that the rule of using the later date of the window does not conflict with any protocol-specified procedure that has to be done pre-infusion (eg, IgG assessments), as all IgG assessments will be performed prior to infusion unless there was a protocol deviation.)

If there is no measurement for a given parameter in an analysis window, data will be considered missing for the corresponding visit.

Efficacy assessments

The schedule for the efficacy assessments is shown in the following table.

Efficacy assessments	Schedule
Recumbent length/height, weight, and head circumference	Every 3 months age < 3 years; every 6 months 3 to <5 years, every 12 months \geq 5 years
Bayley-III	every 6 months ages 1 month to 42 months
Leiter-R/Leiter-3	from final Bayley-III assessment < 42 months of age, every 12 months
GMFM-88	every 6 months age < 5 years; every 12 months \geq 5 years
Pompe PEDI	every 6 months age < 5 years; every 12 months \geq 5 years

Given that patients enter study at different ages, if we define analysis windows for the efficacy endpoints based on the assessment schedule, the definitions will vary depending on each patient's age at study entry. In addition, due to the small patient population, we will focus on individual patient growth by age. The following analysis windows for efficacy assessments will not be used in by-visit summary tables or figures, but may be used in the patient listing to associate observations to the nearest study visits.

Maximum age at signing of the informed consent was 1.9 years.

Table 7 - Analysis window definition for recumbent length/height, weight, and head circumference

Scheduled visit post baseline	Targeted study day	Analysis window in study day

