5.4.4 Unscheduled visits

Unscheduled visit measurements of laboratory data, vital signs, ECG, and ADA will be used for computation of baseline, the last or worst on-treatment value, and analysis according to PCSAs.

The measured values of unscheduled visits will only be included in the by-visit summaries if they are re-allocated to scheduled visits based on the visit windows defined above.

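### Visit windows choose values by date alone, so unscheduled follow-up tests can replace on-time scheduled values in the by-visit laboratory and ECG tables

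*SAP*

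**What the plan says.** SAP 5.4.3 sets one selection rule for its by-visit analyses:

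- Eligibility: "A measurement (scheduled or unscheduled) will be used if it is available and measurement date is within the analysis window".
- Choice among several: "if multiple assessments are associated to the same time point, the closest from the targeted study day will be used".
- Ties: "if the difference is a tie, the value after the targeted study day will be used".
- Several valid values on one day: "then all the valid values of the day will first be averaged before applying the" closeness and tie rules.

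SAP 5.4.4 confirms the route into the tables: "The measured values of unscheduled visits will only be included in the by-visit summaries if they are re-allocated to scheduled visits" using those windows. Neither section prefers a scheduled value.

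For all laboratory variables and quantitative ECG variables, SAP 4.7.3.1 states that "descriptive statistics for results and changes from baseline will be provided for each planned visit during the on-treatment period".

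The protocol says when extra tests arise. Section 9.3.5, on clinically significant laboratory findings: "The Investigator will continue to monitor the patient with additional laboratory assessments until (1) values have reached normal range and/or Baseline", or until the investigator judges the out-of-range values unrelated to treatment or study procedures. Section 9.3.4 has a parallel rule for ECGs, ending at return to baseline or when the investigator finds follow-up no longer necessary. On IgG, Table 9-1 footnote 10 says: "Additional testing should be performed upon determination of any notable deterioration in a patient's motor function".

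**The concern.** Selecting by distance to target is harmless when the competing values arise independently of the results. Here they often do not. Under Protocol 9.3.4 and 9.3.5 an unremarkable scheduled result prompts no follow-up, whereas a clinically significant one does. Only the abnormal scheduled values then face a competitor that can push them out of the visit table.

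A typical path is an abnormal scheduled test taken before the target day, with its repeat falling closer to target. The visit row then carries the repeat. The original value leaves that visit's mean, median, minimum and maximum, although it was on time under the protocol's ±60 days.

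These are the only tables planned for level and change from baseline in laboratory and ECG variables, and safety is the secondary objective. The PCSA table uses every measurement but reports incidence only, so it does not correct the by-visit summaries.

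**Working it through.** The documents give no displacement figure to reproduce, so the rule is applied directly.

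**Inputs from the documents**
- Conduct window of ±60 days around each 12-monthly laboratory and ECG visit (Protocol 9.1; SAP 5.4.3).
- Closest to target is used, and a tie goes to the later value (SAP 5.4.3).
- Week 156 IgG window: Days 915 to 1279, target 1096 (SAP Table 10).
- 12 patients enrolled, 7 withdrawn or dead in less than 4 years (SAP 5.2).

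**Assumptions not in the documents**
- The scheduled day d, relative to target, is equally likely over the permitted days.
- One repeat is taken r days later.
- The laboratory and ECG analysis window is symmetric about the target.

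**Step 1. Chance of replacement, given that a repeat exists.** The repeat at d + r wins when |d + r| ≤ |d|, that is, when d ≤ −r/2.

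| Lag r (days) | d over ±60 (121 days) | d over ±14 (29 days) |
|---|---|---|
| 14 | 54/121 = 45% | 8/29 = 28% |
| 28 | 47/121 = 39% | 1/29 = 3% |
| 56 | 33/121 = 27% | 0/29 = 0% |

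The continuous form for ±60 days, (60 − r/2)/120, gives 44%, 38% and 27%. A winning repeat is no further from target than the value it replaces. Any symmetric window that holds the scheduled value therefore holds the repeat, and the exact window width does not matter.

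**Step 2. Illustrative shift in a visit mean.** Give the variable SD 1 and correlation ρ between scheduled and repeat values. Assume a repeat follows when the scheduled value exceeds a cut-off c, which happens with probability q. With P from the continuous form and φ the standard normal density, the shift is −P(1 − ρ)φ(c).
- Largest in the range tried (q = 20%, ρ = 0.3, r = 14): −0.442 × 0.7 × 0.280 = −0.087 SD.
- Smallest (q = 5%, ρ = 0.9, r = 60): −0.25 × 0.1 × 0.103 = −0.003 SD.

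Simulation over q of 5% to 20%, ρ of 0.3 to 0.9 and lags of 14 to 60 days gave the same ends. The share of values beyond the cut-off fell from 20% to between 14.1% and 18.7%, or from 5% to between 3.1% and 4.5%.

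**Step 3. IgG, if titers are tabulated by Table 10 visit.** Take one unscheduled sample on a random day of the 365-day Week 156 window and a scheduled sample spread evenly over ±60 days. On average 60 of the 365 days beat the scheduled sample: 60/365 = 16%. In the quarterly Week 52 window, with both samples inside, simulation gives 49%.

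**Step 4. Weight of one value.** One replaced value is 1/12 = 8% of a visit mean with all patients present, and 1/5 = 20% with the 12 − 7 = 5 who were not out before 4 years.

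**The case against.** Several counter-arguments have force.

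- **The rule looks at dates, not results.** A reader might infer that the tables are selected by outcome. The documents do not support that: the rule ignores the value, and only the existence of a competitor depends on outcome. Closest to target is also a prespecified rule with a sensible aim, comparable time on study. What remains is a one-sided path by which abnormal values can drop out.
- **Laboratory and ECG data have no tabulated analysis window.** Tables 7 to 11 cover growth, the developmental and motor scales, IgG and Hex4. Since 5.4.4 refers to windows already defined, one could read it as keeping unscheduled laboratory and ECG values out of the by-visit tables altogether. But 5.4.3 applies its windows to by-visit safety analyses, and 5.4.4 names laboratory and ECG data when it covers unscheduled measurements. The ambiguity is real and should be closed.
- **IgG is weaker ground.** A reader might infer that by-visit titer tables are pulled toward values at deterioration. SAP 4.8.1 states no by-visit titer table, and nothing shows which way such samples would move titers. The random-day assumption is doubtful as well, because footnote 5 ties this testing to the developmental and motor assessments. After Month 24, a mid-year motor visit lies at least 182 − 60 = 122 days from the annual IgG target, so it cannot displace a scheduled sample within 60 days.
- **Repeats need not be resolved values.** Investigator judgment can end follow-up earlier, so the drift toward normal is a tendency.
- **The information is not lost.** Clinically significant changes are recorded as AEs, PCSA uses the worst of all measurements, abnormal ECG incidence is tabulated, and the protocol plans patient listings of all safety assessments.

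**Conclusion.** The concern holds in a limited form. The SAP lets an unscheduled value replace an on-time scheduled one, or be averaged with it on the same day. The protocol makes many of those extra laboratory tests and ECGs follow clinically significant changes. The by-visit laboratory and quantitative ECG summaries are therefore open to outcome-dependent replacement, tending toward more normal values. IgG is affected only if titers are summarized by Table 10 visit, with direction unknown.

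The 27% to 45% range is conditional on a repeat existing and on scheduled dates spread evenly over ±60 days; with dates within ±14 days it falls to between 0% and 28%. The documents give no repeat rate, so the number of affected values cannot be stated. The mean shifts of 0.003 to 0.087 SD are illustrative.

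The analyses are descriptive, in at most 12 patients. The efficacy windows are not used for by-visit tables or figures, so efficacy results are untouched. The change is worth making because it is cheap and removes the path, not because a conclusion depends on it.

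**What to change.** In SAP 5.4.3 and 5.4.4, state that:

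1. A scheduled value in the visit's analysis window and within the protocol's ±60 days of target is used for that visit (the closest, if more than one).
2. An unscheduled value is used only when no such scheduled value exists.
3. Scheduled and unscheduled values from the same day are not averaged.
4. Laboratory and ECG visits have stated target days and analysis windows to which these rules apply.

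The ±60-day limit in item 1 matters for IgG. The annual windows run to about ±182 days, and without the limit a scheduled sample far off target would override an unscheduled one close to it.

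Keep all unscheduled values for PCSA and for worst, last and peak values, so no safety signal is lost. With item 1 in place, an on-time scheduled value can no longer be displaced by an unscheduled one.

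The cost is a few sentences, a short table of laboratory and ECG windows, and a sort flag in the programs. The downside is that the chosen value will sometimes lie further from the target day than an available unscheduled one.

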4.5 TERTIARY/EXPLORATORY ENDPOINT(S) ANALYSIS

4.5.1 *Definition of endpoint(s)*

Urinary oligosaccharide (Hex4) levels will be measured by a central laboratory every 6 months to study month 24 and then every 12 months after that.

4.5.2 *Main analytical approach*

Nominal and change from baseline will be summarized by visit.

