Screening/Baseline	-30 to -1	
Week 13	91	[46, 136]
Week 26	182	[137, 227]
Week 39	273	[228, 319]
Week 52	365	[320, 456]
Week 78	547	[457, 638]
Week 104	730	[639, 821]
Week 130	912	[822, 1003]
Week 156	1095	[1004, 1277]

Scheduled visit post baseline	Targeted study day	Analysis window in study day
Week 208	1460	[1278, 1642]
Week 260	1825	[1643, 2007]
Week 312	2190	[2008, 2372]
Week 364	2555	[2373, 2737]
Week 416	2920	[2738, 3102]
Week 468	3285	[3103, 3467]
Week 520	3650	[3468, 3650]

Study days are calculated considering Day 0 as the day of first administration of intervention.

Table 8 - Analysis window definition for Bayley-III and Leiter-R/Leiter-3

Scheduled Visit	Targeted study day	Analysis window in study day
Screening/Baseline	-30 to -1	
Week 26	182	[91, 273]
Week 52	365	[274, 547]
Week 104	730	[548, 912]
Week 156	1095	[913, 1277]
Week 208	1460	[1278, 1642]
Week 260	1825	[1643, 2007]
Week 312	2190	[2008, 2372]
Week 364	2555	[2373, 2737]
Week 416	2920	[2738, 3102]
Week 468	3285	[3103, 3467]
Week 520	3650	[3468, 3650]

Study days are calculated considering Day 0 as the day of first administration of intervention.

Table 9 - Analysis window definition for GMFM-88 and Pompe PEDI

Scheduled Visit	Targeted study day	Analysis window in study day
Screening/Baseline	-30 to -1	
Week 26	182	[91, 273]
Week 52	365	[274, 456]

Scheduled Visit	Targeted study day	Analysis window in study day
Week 78	547	[457, 638]
Week 104	730	[639, 821]
Week 130	912	[822, 1003]
Week 156	1095	[1004, 1277]
Week 208	1460	[1278, 1642]
Week 260	1825	[1643, 2007]
Week 312	2190	[2008, 2372]
Week 364	2555	[2373, 2737]
Week 416	2920	[2738, 3102]
Week 468	3285	[3103, 3467]
Week 520	3650	[3468, 3650]

Study days are calculated considering Day 0 as the day of first administration of intervention.

Safety and other exploratory assessments

Safety and other exploratory assessments are supposed to be conducted every 12 months with a window of \pm 60 days, except for Serum IgG collection and urine Hex4.

- Neuroimaging assessment
- Hearing testing
- Visual screening
- ECG
- Safety laboratory assessments
- Serum IgG collection (every 3 months to study month 24 and then every 12 months after that)
- Urine Hex4 (every 6 months to study month 24 and then every 12 months after that)

Table 10 - Analysis window definition for serum IgG visits

Scheduled Visit	Visit window defined in protocol (\pm 60 days)	Target study day	Analysis window in study day
Screening/Baseline	Day -30 to -1		-30 to -1

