Week 13	Month 3	91	1 to 137
Week 26	Month 6	183	138 to 229
Week 39	Month 9	274	230 to 320
Week 52	Month 12	365	321 to 411
Week 65	Month 15	456	412 to 502
Week 78	Month 18	548	503 to 594

Scheduled Visit	Visit window defined in protocol (± 60 days)	Target study day	Analysis window in study day
Week 91	Month 21	639	595 to 685
Week 104	Month 24	731	686 to 914
Week 156	Month 36	1096	915 to 1279
Week 208	Month 48	1461	1280 to 1644
Week 260	Month 60	1826	1645 to 2009
Week 312	Month 72	2192	2010 to 2375
Week 364	Month 84	2557	2376 to 2740
Week 416	Month 96	2922	2741 to 3105
Week 468	Month 108	3287	3106 to 3470
Week 520	Month 120	3653	3471 to 3836

Study days are calculated considering Day 0 as the day of first administration of intervention.

Table 11 - Analysis window definition for urine Hex4

Scheduled Visit	Visit window defined in protocol (± 60 days)	Target study day for analysis windows	Range of study days for analysis window
Screening/Baseline	Day -30 to -1		-30 to -1
Week 26	Month 6	183	1 to 274
Week 52	Month 12	365	275 to 457
Week 78	Month 18	548	458 to 640
Week 104	Month 24	731	641 to 1096
Week 156	Month 36	1096	1097 to 1461
Week 208	Month 48	1461	1462 to 1826
Week 260	Month 60	1826	1827 to 2192
Week 312	Month 72	2192	2193 to 2557
Week 364	Month 84	2557	2558 to 2922
Week 416	Month 96	2922	2923 to 3287
Week 468	Month 108	3287	3288 to 3653
Week 520	Month 120	3653	3654 to 4018

Study days are calculated considering Day 0 as the day of first administration of intervention.

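### From Month 36 on, every Hex4 window in SAP Table 11 excludes its own target day, so samples taken on or before target are put under the previous year's visit or dropped

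*SAP*

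**What the plan says.** SAP 4.5.2 gives the only planned Hex4 analysis: "Nominal and change from baseline will be summarized by visit". Sampling is "every 6 months to study month 24 and then every 12 months after that" (SAP 5.4.3). Protocol section 9.1 and Table 9-1 allow ±60 days around these visits.

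SAP 5.4.3 says how a sample is assigned to a visit. On the role of the windows: "The following analysis windows will decide how the scheduled and/or unscheduled visits will be used in the by-visit analyses of efficacy, safety, and exploratory variables". On use of a value: "A measurement (scheduled or unscheduled) will be used if it is available and measurement date is within the analysis window". On several values in one window: "if multiple assessments are associated to the same time point, the closest from the targeted study day will be used". On an empty window: "If there is no measurement for a given parameter in an analysis window, data will be considered missing for the corresponding visit".

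The Hex4 windows are in "Table 11 - Analysis window definition for urine Hex4". Up to Month 24 each window surrounds its target. After that, each window starts one day after its target and ends on the target of the following visit. The Month 24 window itself (641 to 1096) ends on the Month 36 target day.

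**The concern.** A visit window should contain the day on which the visit is due. Here 8 of the 12 post-baseline Hex4 windows do not. The windows are contiguous, so a sample taken on or before its yearly target falls into the previous visit's window, and nothing else in SAP 5.4.3 returns it to the right visit.

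By-visit summaries of the growth, motor and cognitive endpoints were removed in SAP version 2.0, which leaves Hex4 as the only efficacy-type measure still summarised numerically by visit. A literal implementation would show part of its long-term course a year too early, mix two yearly visits in one column, and report missing visits for patients who were sampled on schedule.

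**Working it through.** **Inputs.** Targets and windows are from SAP Tables 10 and 11, the ±60 days from Protocol 9.1, and the assignment rules from SAP 5.4.3.

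**Step 1: are the targets right?** Target = months × 30.4375, the month length used in SAP 5.4.1. For Month 36, 36 × 30.4375 = 1095.75, or 1096. For Month 120, 120 × 30.4375 = 3652.5, or 3653. The targets are sound; the fault is in the windows.

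**Step 2: does each window contain its target?** The test is lower bound ≤ target ≤ upper bound.

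| Visit | Target | Table 11 window | Target inside? | Window holding the target | Table 10 window |
|---|---|---|---|---|---|
| Month 24 (Week 104) | 731 | 641–1096 | yes | Month 24 | 686–914 |
| Month 36 (Week 156) | 1096 | 1097–1461 | no | Month 24 | 915–1279 |
| Month 48 (Week 208) | 1461 | 1462–1826 | no | Month 36 | 1280–1644 |
| Month 60 (Week 260) | 1826 | 1827–2192 | no | Month 48 | 1645–2009 |
| Month 72 (Week 312) | 2192 | 2193–2557 | no | Month 60 | 2010–2375 |
| Month 84 (Week 364) | 2557 | 2558–2922 | no | Month 72 | 2376–2740 |
| Month 96 (Week 416) | 2922 | 2923–3287 | no | Month 84 | 2741–3105 |
| Month 108 (Week 468) | 3287 | 3288–3653 | no | Month 96 | 3106–3470 |
| Month 120 (Week 520) | 3653 | 3654–4018 | no | Month 108 | 3471–3836 |

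Months 6, 12 and 18 contain their targets in Table 11. All 16 post-baseline windows in Table 10 contain theirs, as do all windows in Tables 7 to 9.

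**Step 3: is it a deliberate convention?** Table 11's own early boundaries are midpoints between targets: (183 + 365)/2 = 274, (365 + 548)/2 = 456.5 (table: 457), (548 + 731)/2 = 639.5 (table: 640). The midpoint rule stops at the upper bound of Week 104, where (731 + 1096)/2 = 913.5 is replaced by 1096. Table 10 keeps it at 914.

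**Step 4: a patient sampled on every target day.** The Month 24 window receives days 731 and 1096 and keeps 731, so the Month 36 sample is dropped. Day 1461 (Month 48) is reported as Month 36, day 1826 (Month 60) as Month 48, and so on until day 3653 (Month 120) is reported as Month 108. Month 120 is missing. The result is the same if every sample is taken 30 or 60 days early. If every sample is 1 to 60 days late, all are placed correctly.

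**Step 5: across the permitted ±60 days.** At each yearly visit from Month 36, the 60 late days go to the right visit and the 61 days on or before target to the wrong one: 60/121 = 49.6% right. At Months 6, 12, 18 and 24 it is 121/121.

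**Step 6: illustration with an assumed timing pattern.** The documents give no data on visit timing. Assume that each visit falls uniformly and independently on the 121 permitted days and that no visit is missed. For Weeks 156 to 468:

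- right sample: own visit late, 60/121 = 49.6%. If the next year's sample also falls in the window, the patient's own is closer to target and is kept.
- next year's sample: both visits on or before target, (61/121)² = 25.4%.
- nothing: own visit on or before target and next visit late, (61/121)(60/121) = 25.0%.

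Week 520 is empty in 61/121 = 50.4%. The expected number of samples left out of the summary per fully attending patient is 61/121 for Month 36 plus 7 × (61/121)(60/121) for Months 48 to 120, that is 0.504 + 1.750 = 2.25.

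**The case against.** The arithmetic is hard to contest, but its importance can be. Hex4 is a tertiary, descriptive endpoint with no test attached. The primary endpoints are shown as listings and plots by age, and IgG has its own sound table, so the primary, safety and immunogenicity results are untouched. SAP 5.2 reports 12 patients enrolled, of whom 7 withdrew or died in under 4 years. That leaves about 5 from Month 48 on, and a mean over 5 children carries little weight even with correct windows. Protocol section 11 also makes summary tables conditional on the data not being too sparse, and has all data listed, so no value disappears from the report. Samples 1 to 60 days late are placed correctly. The 50/25/25 split depends on an assumed timing pattern: misplacement could run from 0% (all visits late) to 100% (all on or before target).

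These points limit the reach of the error and should be stated with it. With perfect on-target attendance, the only value dropped is Month 36; the later ones are relabelled. None of this makes the table correct. With about 5 patients per column, one mislabelled or absent value visibly changes the n and the mean, so the small cohort is also a reason to correct it.

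**Conclusion.** The concern holds. All 8 yearly Hex4 windows from Month 36 to Month 120 exclude their own target, and under the rules of SAP 5.4.3 every sample taken on or before target goes to the previous visit. That covers 61 of the 121 permitted days at each of those visits. This result rests only on the tables and the ±60-day tolerance. The split of about 50% right, 25% next year's sample and 25% empty rests in addition on uniform, independent timing and full attendance.

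That this is a slip in construction is an inference, but a strong one: the pattern is regular over eight rows, and it contradicts Table 11's own earlier rows and Table 10's windows for the same target days. The by-visit Hex4 summary should not be programmed from Table 11 as it stands.

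**What to change.** Change nine window entries in SAP Table 11:

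| Visit | Replacement window |
|---|---|
| Week 104 | 641–914 |
| Week 156 | 915–1279 |
| Week 208 | 1280–1644 |
| Week 260 | 1645–2009 |
| Week 312 | 2010–2375 |
| Week 364 | 2376–2740 |
| Week 416 | 2741–3105 |
| Week 468 | 3106–3470 |
| Week 520 | 3471–3836 |

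The rows from Week 156 on are Table 10's. For Week 104 the lower bound stays at Table 11's 641, because Table 10's 686 reflects an IgG visit at Month 21 that Hex4 does not have; only the upper bound moves, to Table 10's 914. With these windows, 121 of 121 permitted days are placed correctly at all 12 visits.

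The cost is an edit to one table and the matching program code, with no new data or assumption. The last window would end at day 3836 instead of 4018, which loses nothing within tolerance: the latest permitted Month 120 sample is day 3653 + 60 = 3713.
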